4.7 End of study definition

The end of the study is defined as the date of the last visit CCI

Study completion is defined as when the total number of primary events (collection of parasite clearance time for all patients) are obtained from all cohorts and when the last patient finishes their last study visit and any repeat assessments associated with this visit have been documented and followed-up appropriately by the investigator (e.g., Each patient will be required to complete the study in its entirety, and thereafter no further study treatment will be made available to them in the scope of the trial).

All randomized and/or treated patients should have a safety follow-up call conducted at least 30 days after last administration of study treatment. This follow-up may be a phone call or a

study site visit. The information collected is kept as source documentation. SAE reporting continues during this time period as described in [Section 8.6.3](#). Documentation of attempts to contact the patient are required to be recorded in the source documentation.

5 Study Population

The study population will consist of adult and adolescent male and female patients.

IMPORTANT

The inclusion/exclusion criteria for the core protocol are located in these sections ([Section 5.1](#) and [Section 5.2](#)). These criteria apply to all patients enrolled into this study. No additional criteria should be applied by the investigator, in order to ensure that the study population will be representative of all eligible patients. However, there may also be additional agent specific inclusion/exclusion criteria for each of the investigational compounds, which are provided in [Section 12](#).

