5.2 Exclusion criteria

Part A:

Patients meeting any of the following criteria are not eligible for inclusion in this part of the study.

1. Patients with signs and symptoms of severe/complicated malaria at screening
2. Mixed *Plasmodium* infection (i.e., infection with more than one malaria species) at screening
3. Use of any anti-malarial treatment or antibiotics with anti-malarial activity (or prohibited medication) in the preceding 14 days or at least 5 half-lives whichever is longer before screening
4. Moderate to severe anemia, chronic hemoglobinopathy (Hemoglobin level < 8 g/dL), or known chronic underlying disease such as sickle cell disease at screening
5. Active infections including tuberculosis, or history of taking anti-tuberculosis medications within 12 months prior to screening
6. History of, or current alcohol use disorder defined as five or more drinks on the same occasion on each of 5 or more days in the past 30 days prior to screening
7. Known clinically significant liver disease (e.g., chronic hepatitis, liver cirrhosis (compensated or decompensated), history of hepatitis B or C, hepatitis A or B vaccination in the last 3 months, known gallbladder or bile duct disease, acute or chronic pancreatitis.

Clinical or laboratory evidence of any of the following at screening:

- AST/ALT > 3 x the upper limit of normal range (ULN), regardless of the level of total bilirubin
 - AST/ALT > 1.5 and ≤ 2 x ULN and total bilirubin is $> \text{ULN}$
 - Total bilirubin > 2 x ULN, regardless of the level of AST/ALT
8. Any known/suspected immunosuppressive or immunodeficient condition, including human immunodeficiency virus (HIV) infection at screening
 9. Known disturbances of uncorrected electrolyte balance, e.g., hypokalemia, hypocalcemia or hypomagnesemia
 10. Severe malnutrition (Body Mass Index (BMI) < 16.0) at screening
 11. Severe vomiting, defined as more than 3 times in the 24 hours prior to screening or severe diarrhea defined as watery stools more than 3 times in the 24 hours prior to screening
 12. Pregnant or nursing (lactating) women

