13. Women of child-bearing potential, defined as all women physiologically capable of becoming pregnant, unless they are using methods of contraception defined in the cohort-specific sections (Section 12). Women are considered post-menopausal if they have had 12 months of natural (spontaneous) amenorrhea with an appropriate clinical profile (e.g., age-appropriate history of vasomotor symptoms). Women are considered not of child-bearing potential if they are post-menopausal or have had surgical bilateral oophorectomy (with or without hysterectomy), total hysterectomy or bilateral tubal ligation at least six weeks prior to enrollment on study. In the case of oophorectomy alone, only when the reproductive status of the woman has been confirmed by follow-up hormone level assessment is she considered to be not of child-bearing potential.
14. Sexually active patients not willing to practice effective contraception. Sexually active males must use a condom during intercourse while taking treatment and for at least 30 days after stopping study treatment. A condom is required for **all** sexually active male patients to prevent them from fathering a child AND to prevent delivery of study treatment via seminal fluid to their partner. In addition, male patients must not donate sperm for the time period specified above. If local regulations are more stringent than the contraception methods listed above to prevent pregnancy, local regulations apply and will be described in the ICF.
15. History or current diagnosis of ECG abnormalities indicating significant risk of safety for patients participating in the study such as:
 - Concomitant clinically significant cardiac arrhythmias, e.g., sustained ventricular tachycardia, and clinically significant second or third degree AV block without a pacemaker
 - History of familial long QT syndrome or known family history of Torsades de Pointe
 - Resting heart rate (physical exam or 12 lead ECG) < 60bpm
16. Resting QTcF > 450 msec (males), QTcF > 460 msec (females) at screening
17. Use of agents known to prolong the QT interval unless they can be permanently discontinued for the duration of study
18. Any surgical or medical condition which might significantly alter the absorption, distribution, metabolism, or excretion of drugs, or which may jeopardize the patient in case of participation in the study. The investigator should make this determination in consideration of the patient's medical history, clinical and/or laboratory result

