19. History of malignancy of any organ system (other than localized basal cell carcinoma of the skin or *in situ* cervical cancer), treated or untreated, within the past 5 years of screening, regardless of whether there is evidence of local recurrence or metastases
20. Patients with serum creatinine $\geq 2 \times$ ULN in the absence of dehydration at screening. In case of dehydration, patients with serum creatinine $\geq 2 \times$ ULN after oral or parenteral rehydration
21. Patients taking drugs that are strong inducers of CYP3A4 such as rifampicin, carbamazepine, phenytoin, St. John's wort (*Hypericum perforatum*) at screening
22. History of hypersensitivity to any of the study treatments or its excipients or to drugs of similar chemical classes
23. Use of herbal medication within one week of screening

24. Use of other investigational drugs within 5 half-lives of screening, or within 30 days or until the expected pharmacodynamic (PD) effect has returned to baseline, whichever is longer; **or longer if required by regulations.**
25. Previous participation in any malaria vaccine study or received malaria vaccine in any other circumstance
26. Previous participation in the same cohort within this study

Part B:

Patients meeting any of the following criteria are not eligible for inclusion in this part of the study.

The same exclusion criteria from Part A apply in Part B with the addition of the following:

1. Women of child-bearing potential, defined as all women physiologically capable of becoming pregnant, unless they are using methods of contraception defined in the cohort-specific sections ([Section 12](#)). Additionally, for combination therapy in Part B, the more conservative contraception requirement will be used.

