5.4 Screen failures

A screen failure occurs when a patient who consents to participate in the clinical study is subsequently found to be ineligible and therefore not randomly assigned to treatment/entered in the study. A minimal set of screen failure information is required to ensure transparent reporting of screen failure patients to meet the Consolidated Standards of Reporting Trials (CONSORT) publishing requirements and to respond to queries from regulatory authorities. Minimal information includes demography, screen failure details, eligibility criteria, and any serious adverse event (SAE).

Patients who sign an informed consent form and are subsequently found to be ineligible prior to randomization will be considered as screen failures. The reason for screen failure should be recorded on the appropriate Case Report Form. The demographic information, informed consent, and Inclusion/Exclusion pages must also be completed for screen failure patients. No other data will be entered into the clinical database for patients who are screen failures, unless the patient experienced a serious adverse event during the screening period (see [Section 8.6](#) for reporting details). If the patient fails to be randomized, the Interactive Response Technology (IRT) must be notified within 2 days of the screen fail that the patient was not randomized. Data and samples collected from patients prior to screen failure may still be analyzed.

Patients who are randomized and fail to start treatment, e.g., patients randomized in error, will be considered early terminators. The reason should be recorded on the appropriate Case Report Form.

It is not permissible to re-screen a patient within the same malaria episode if they fail the initial pre-screening or screening. Re-screening of a previously screen failed patient may occur in case the patient is returning to the study site for a new malaria episode. A new subject number will be issued to the patient.

Patients not meeting eligibility criteria at a particular malaria episode will receive an anti-malarial treatment as per local standards.

In the case where a safety laboratory assessment at screening is outside of the range specified in the eligibility criteria, the assessment may be repeated once prior to randomization. If the repeat value remains outside of the specified range, the patient must be excluded from the study.

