8.4.4 Clinical safety laboratory tests

As per [Section 4.6](#), during a public health emergency as declared by local or regional authorities' i.e., pandemic, epidemic or natural disaster, that limits or prevents on-site study visits, if patients cannot visit the site for protocol-specified safety lab assessments, an alternative lab (local) collection site may be used.

Clinically significant abnormalities must be recorded as either medical history/current medical conditions or adverse events as appropriate.

In the case where a laboratory range is not specified by the protocol, but a value is outside the reference range for the laboratory at screening, a decision regarding whether the result is of clinical significance or not shall be made by the investigator (in consultation with the Sponsor) and shall be based, in part, upon the nature and degree of the observed abnormality. The assessment may be repeated once prior to randomization.

All abnormal lab results must be evaluated for criteria defining the inclusion/exclusion criteria, an adverse event and reported as such if the criteria are met. For those lab adverse events, repeated evaluations are mandatory until normalization of the result(s) or until the result is no longer considered to be clinically significant.

In all cases, the investigator must document in the source documents, the clinical considerations (i.e., result was/was not clinically significant and/or medically relevant) in allowing or disallowing the patient to continue in the study.

Local laboratories will be used for analysis of safety specimens.

Urinalysis

A midstream urine sample (approx. 30 mL) will be obtained, in order to avoid contamination with epithelial cells and sediments, and allow proper assessments.

Special clinical laboratory evaluations

All abnormal lab results must be evaluated for criteria defining an adverse event and reported as such if the criteria are met. For those lab adverse events, repeated evaluations are mandatory until normalization of the result(s) or until the result is no longer considered to be clinically significant.

Table 8-2 Laboratory assessments

The CCI logo is displayed in red text on a black rectangular background.

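### Exclusion criterion 7 leaves a gap in its liver limits: AST and ALT both >2 to 3 x ULN with bilirubin >1 to 2 x ULN meets no numeric bullet, although lower enzymes at the same bilirubin are excluded

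*Protocol*

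**What the plan says.** Protocol 5.2, Part A, criterion 7 opens with a diagnosis-based exclusion, "Known clinically significant liver disease", and then lists three laboratory findings at screening. Any one of them excludes:

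- (a) "AST/ALT > 3 x the upper limit of normal range (ULN), regardless of the level of total bilirubin"
- (b) "AST/ALT > 1.5 and ≤ 2 x ULN and total bilirubin is" above ULN
- (c) total bilirubin above 2 x ULN, whatever the AST/ALT.

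The protocol summary gives the same three bounds under key exclusion criteria. Part B takes them over: "The same exclusion criteria from Part A apply in Part B with the addition of the following". The additional exclusion criteria that can be read for Cohorts A1, B1 and B2 in Section 12 concern contraception and set no liver limit. Other parts of Section 12 are redacted.

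Four other provisions bear on how the rule works in practice:

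- Criterion 18 excludes conditions that could alter drug disposition "or which may jeopardize the patient in case of participation in the study". It tells the investigator to weigh history, clinical findings and laboratory results.
- The note at the start of Section 5 says: "No additional criteria should be applied by the investigator".
- Section 5.4 allows one repeat of an out-of-range safety laboratory test before randomization: "If the repeat value remains outside of the specified range, the patient must be excluded from the study".
- Section 8.4.4 gives the investigator, in consultation with the sponsor, a decision on clinical significance. It does so for a stated case: "In the case where a laboratory range is not specified by the protocol".

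**The concern.** Bullet (b) shows the intent. When bilirubin is raised, the tolerated enzyme level should be lower than the general limit of 3 x ULN. As written, that tighter limit applies only up to 2 x ULN, and nothing takes over until 3 x ULN. A rule of this kind should not turn from exclude to pass as a liver value worsens, and this one does. The protocol gives no reason for it.

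What is at stake is screening safety and consistency between sites. In Part A and in the investigational arm of Part B the treatment is a single dose, and Section 7.1 says that discontinuation does not apply there. Eligibility is therefore the main preventive control on liver risk. If sites must rely on judgement for this combination of values, two sites may decide differently on the same results.

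**Working it through.** No figure in the plan needs reproducing. The check is whether the three bullets cover the range without a break.

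**Rule.** Values are in multiples of ULN. Let both enzymes equal E and let total bilirubin be T. A patient is excluded if

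- (a) E > 3, or
- (b) 1.5 < E ≤ 2 and T > 1, or
- (c) T > 2.

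**Where the break lies.** Take 1 < T ≤ 2, so that (c) is not met.

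- 1.5 < E ≤ 2: (b) is met, so the patient is excluded.
- 2 < E ≤ 3: (b) fails on its upper bound and (a) is not reached, so no bullet applies.
- E > 3: (a) is met, so the patient is excluded.

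At T = 1.5:

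| AST = ALT (x ULN) | Bullet met now | With the upper bound in (b) deleted |
|---|---|---|
| 1.8 | (b) | excluded |
| 2.2 | none | excluded |
| 2.8 | none | excluded |
| 3.1 | (a) | excluded |

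**Grid check, equal enzymes, steps of 0.1 x ULN.**

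- E 1.6 to 2.0 (5 values) by T 1.1 to 2.0 (10 values): 5 × 10 = 50 combinations, all 50 excluded.
- E 2.1 to 3.0 by the same T: 10 × 10 = 100 combinations, none excluded.
- One-step reversals (excluded at E, not excluded at E + 0.1): 10, one at each T from 1.1 to 2.0, all between E = 2.0 and 2.1.
- With the upper bound in (b) deleted: 100 of 100 excluded and no reversals. With E 2.1 to 3.0 and T 0.1 to 1.0 (bilirubin not above ULN), 0 of 100 are excluded, as now.

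These counts describe combinations under the rule, not patients.

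**Discordant enzymes.** AST/ALT could mean either enzyme, both enzymes or the higher one. With equal enzymes the three readings coincide. With unequal enzymes they may not. Take AST 2.5, ALT 1.8, T 1.5:

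| Reading | Now | Upper bound in (b) deleted |
|---|---|---|
| Either enzyme | excluded: ALT 1.8 meets (b) | excluded |
| Both enzymes | not excluded: AST 2.5 is above 2 | excluded |
| Higher enzyme | not excluded: 2.5 is above 2 | excluded |

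**Why deleting the bound is enough.** Without it, every bullet has only lower limits: E > 3; E > 1.5 with T > 1; T > 2. A higher value can then never release a patient whom a lower value excludes, under any of the three readings. Both enzymes >2 to 3 also implies both >1.5, so bullet (b) captures the whole demonstrated gap.

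**The case against.** The strongest case against is that a patient of concern can already be kept out. Criterion 18 is a listed exclusion and expressly lets the investigator consider laboratory results. The Section 5 note bars added criteria, not the use of listed ones. Section 8.4.4 also requires the investigator to document why a patient was allowed to continue or not. Those points stand. A reader might infer that the protocol obliges sites to enrol these patients, and the documents do not support that. What remains is that none of these routes sets a liver threshold. The diagnosis-based part of criterion 7 does not clearly reach an isolated laboratory finding. The Section 8.4.4 decision route is arguable here, because ranges are specified.

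A reader might also infer that every patient with AST/ALT >2 to 3 x ULN and mildly raised bilirubin passes. That goes too far. With AST 2.5, ALT 1.8 and bilirubin 1.5 x ULN, the either-enzyme reading already excludes the patient. The gap is certain only when both enzymes lie in >2 to 3 x ULN.

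The repeat test could in principle turn an exclusion into a pass, if both enzymes rose from 1.8 to 2.2 x ULN with bilirubin at 1.5 x ULN. This needs a worsening result that the site accepts as back in range, and it adds no defect beyond the gap itself.

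Finally, the exposure is bounded. The gap ends at the enzyme and bilirubin cut-offs of the protocol's potential Hy's Law definition (>3 x ULN and >2 x ULN, Appendix 1). Patients stay at the site for at least 3 days, liver events are followed up, and a DMC reviews data. This limits the risk but does not explain the break in the rule.

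**Conclusion.** The point holds for the supplied protocol text. With AST and ALT both >2 to 3 x ULN and total bilirubin >1 to 2 x ULN, no numeric bullet of criterion 7 applies, although both enzymes >1.5 to 2 x ULN at the same bilirubin are excluded. Such patients can be excluded only by judgement. The same bounds in the protocol summary make a text-extraction error in the 2 x ULN limit unlikely.

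The conclusion assumes that the redacted parts of Section 12 add no liver threshold for a given cohort. If they do, that cohort may be covered, but the core bullets would still not meet.

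This is a drafting fault in a safety criterion that should be corrected. It would be wrong to infer that it affects the efficacy results: no endpoint, estimand or sample size depends on it. The number of patients who would fall in the gap cannot be derived. Nor can it be said that the wording is still in force, because the supplied protocol ends with the June 2023 amendment and the SAP rests on version 03 of 20-Mar-2024.

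**What to change.** 1. Check whether protocol version 03 (20-Mar-2024) still carries the wording. If it does not, nothing further is needed.
2. If it does, delete the upper bound in bullet (b), so that it reads: *AST/ALT > 1.5 x ULN and total bilirubin > ULN*. Make the change in Section 5.2 criterion 7 and in the protocol summary. Part B follows by reference.
3. Update the eligibility check to match.

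This closes the gap under every reading of AST/ALT and leaves bullets (a) and (c) as they are. Patients with bilirubin at or below ULN are unaffected.

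Two related questions are separate clinical decisions and are not needed to close the gap. One is whether AST/ALT should be spelled out as *AST or ALT*. If the intended meaning is both enzymes, that change would widen bullet (a): AST 3.5 with ALT 1.0 x ULN and normal bilirubin would be newly excluded. The other is whether the cap in (a) should be 2 x ULN. That would also exclude enzymes >2 to 3 x ULN with bilirubin at or below ULN (100 of 100 such combinations on the equal-enzyme grid, against none now). The documents do not show which bound was intended.

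The cost is a one-phrase edit in two places, the eligibility check, and some additional screen failures whose number cannot be derived.

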5.3 Restrictions for study participants

For the duration of the study, patients should be informed and reminded of the restrictions outlined in this section.

5.3.1 Dietary restrictions

Food restrictions for individual cohorts will be described in [Section 12](#).

Patients taking Coartem in Part B should follow prescribing information. Coartem should be taken with food as per product label.

Patients can drink water *ad libitum*; however, to ensure adequate hydration for urine collection (if applicable), patients should have a fluid intake of at least 240 mL every 4 hours during waking hours on Day 1 in addition to fluid taken with meals and medication.

5.3.2 Other restrictions

- Contraception requirements are defined in [Section 5.2](#) and [Section 12](#)
- Other restrictions are outlined in [Section 12](#)

5.4 Screen failures

A screen failure occurs when a patient who consents to participate in the clinical study is subsequently found to be ineligible and therefore not randomly assigned to treatment/entered in the study. A minimal set of screen failure information is required to ensure transparent reporting of screen failure patients to meet the Consolidated Standards of Reporting Trials (CONSORT) publishing requirements and to respond to queries from regulatory authorities. Minimal information includes demography, screen failure details, eligibility criteria, and any serious adverse event (SAE).

Patients who sign an informed consent form and are subsequently found to be ineligible prior to randomization will be considered as screen failures. The reason for screen failure should be recorded on the appropriate Case Report Form. The demographic information, informed consent, and Inclusion/Exclusion pages must also be completed for screen failure patients. No other data will be entered into the clinical database for patients who are screen failures, unless the patient experienced a serious adverse event during the screening period (see [Section 8.6](#) for reporting details). If the patient fails to be randomized, the Interactive Response Technology (IRT) must be notified within 2 days of the screen fail that the patient was not randomized. Data and samples collected from patients prior to screen failure may still be analyzed.

Patients who are randomized and fail to start treatment, e.g., patients randomized in error, will be considered early terminators. The reason should be recorded on the appropriate Case Report Form.

It is not permissible to re-screen a patient within the same malaria episode if they fail the initial pre-screening or screening. Re-screening of a previously screen failed patient may occur in case the patient is returning to the study site for a new malaria episode. A new subject number will be issued to the patient.

Patients not meeting eligibility criteria at a particular malaria episode will receive an anti-malarial treatment as per local standards.

In the case where a safety laboratory assessment at screening is outside of the range specified in the eligibility criteria, the assessment may be repeated once prior to randomization. If the repeat value remains outside of the specified range, the patient must be excluded from the study.

